6.14.4. Clinical Laboratory Evaluation

Clinical laboratory assessments include hematology, serum chemistry, urinalysis, and safety-related immune markers, such as neutrophil counts.

Laboratory test observed values at each visit (starting at baseline) and change from baseline to each scheduled visit, respectively, will be displayed in box plots for patients in the P2 of the Main Study Safety Population who have both a baseline and at least 1 postbaseline result. These box plots will be used to evaluate trends over time and to assess a potential impact of outliers on central tendency summaries.

- The scheduled visits/measurements will be included. The unscheduled visits and the repeat measurements will be excluded.
- The displays with both SI and conventional units will be provided, when different.
- The following summary statistics will be included as a table below the box plot: number of patients with a baseline and at least 1 postbaseline result, mean, SD, minimum, Q1, median, Q3, and maximum.
- Data will be summarized based on original scale.
- On the box plots of the laboratory test observed values, the lines of the reference ranges/limits (by using the large clinical trial population-based reference limits, that is, Lilly reference ranges) will be added. In cases where limits vary across age and gender, the lowest of the high limits and the highest of the low limits will be used.

The number and percentage of patients with a treatment-emergent or follow-up emergent abnormal high or low for laboratory tests will be summarized by treatment group for each safety population. The comparisons between treatment groups will be conducted using Fisher's exact test.

- All scheduled, unscheduled and repeated measurements will be included.
- In general, performing lab reference ranges will be used to define the low and high limits. Alanine aminotransferase (ALT), aspartate aminotransferase (AST), total bilirubin, and alkaline phosphatase (ALP) will not be included in the treatment-emergent abnormal high or low summary as a separate analysis addressing the risk of liver injury is described in [Table RHCD.6.7](#).
- Note that the ranges are defined by a lower limit of normal (LLN) and an upper limit of normal (ULN). A result that is greater than or equal to the LLN and less than or equal to the ULN is considered to be within the normal ranges.
- For categorical laboratory tests:
 - Treatment-emergent abnormal value is defined as a change from normal at all baseline visits to abnormal at any time postbaseline during the treatment period.
 - Follow-up emergent abnormal result is defined as a change from normal at baseline to abnormal at any time during the follow-up period.

- For continuous laboratory tests:
 - Treatment-emergent high value is defined as a change from a value less than or equal to the ULN at all baseline visits to a value greater than the ULN at any time postbaseline during the treatment period.
 - Treatment-emergent low value is defined as a change from a value greater than or equal to the LLN at all baseline visits to a value less than the LLN at any time postbaseline during the treatment period.
 - Follow-up emergent high value is defined as a change from a value less than or equal to the ULN at baseline to a value greater than the ULN at any time postbaseline during the follow-up period.
 - Follow-up emergent low value is defined as a change from a value greater than or equal to the LLN at baseline to a value less than the LLN at any time postbaseline during the follow-up period.

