
To assess the relationship between exposure and efficacy and exposure and immunogenicity
	
 • Model parameters for the exposure-response relationship between ixekizumab serum trough concentrations and efficacy endpoints (for example, sPGA, PASI) at Week 12

Objectives	Endpoints
	
 • Serum trough concentrations for ixekizumab antibody titer subgroups
To assess the safety of ixekizumab	
 • To evaluate the safety of ixekizumab, including but not limited to: infections; injection-site reactions; B-, T-, and NK-cell levels; WBC count; RBC count; and laboratory values (hematology and chemistry [including ALT and AST]) during the course of the study
To demonstrate normal growth and pubertal progression in children treated with ixekizumab during the course of the study	
 • Weight, height, and BMI data will be merged to the Centers for Disease Control and Prevention standard growth data by age and gender to compare subjects' growth with normal values • Shift table for Tanner stage from maximum baseline to maximum postbaseline by gender
To evaluate the genital involvement of the subjects per the questionnaire Binary Questions on Psoriasis Location	
 • Proportion of subjects achieving no psoriasis presence in each psoriasis location
To evaluate the patient's global assessment of disease severity	
 • Proportion of subjects achieving patient's global assessment of disease severity 0 or 1
To evaluate the effect of ixekizumab on maintenance of efficacy and health outcomes during the open-label maintenance period and extension period.	
 • Proportion of subjects achieving PASI 90 • Proportion of subjects achieving sPGA (0) • Proportion of subjects achieving PASI 100 • Proportion of subjects achieving PASI 75 • Proportion of subjects achieving sPGA (0,1) • Improvement ≥ 4 for subjects who had a baseline Itch NRS score ≥ 4

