6.14.3.1. Special Safety Topics including Adverse Events of Special Interest

Safety information on special topics including AEs of special interest (AESIs) will be presented by treatment group for P2 Main Study Safety Population and All Ixekizumab Safety Population.

[Table RHCD.6.7](#) provides the definitions/derivations and analyses methods (including analyses, summaries and by-patient listings) of special safety topics including AESIs.

Potential AESIs will be identified by a standardized MedDRA query (SMQ) or a Lilly-defined MedDRA PT listing. Preferred terms within an SMQ will be classified as broad and narrow. In the Lilly-defined MedDRA PT listings, Lilly has provided the broad and narrow classification. The Lilly-defined broad terms are for a more sensitive search of potential events of interest, and the Lilly-defined narrow terms are for a more specific search. Therefore, the summaries will include the classifications of broad term (same as pooling narrow and broad terms together) and narrow term.

In the event that the listing of terms or analysis changes for a special safety topic, it will be documented in the most current program safety analysis plan (PSAP) which will supersede this document; it will not warrant an amendment to the individual study SAP.

Fisher's exact tests will be used to compare the treatment groups.

In general, AESI summary will not be provided for Follow-Up Population during Period 5 except for cytopenia and hepatic laboratory tests.

Table RHCD.6.7. Definitions and Analyses of Special Safety Topics including Adverse Events of Special Interest

Special Safety Topic	Definition/Derivation	Analysis/Summary/Listing
Hepatic	
Hepatic AE analysis will include events that are potentially drug-related hepatic disorders by using the MedDRA PTs contained in any of the following SMQs:
 
 • Broad and narrow terms in the Liver related investigations, signs and symptoms (20000008) • Broad and narrow terms in the Cholestasis and jaundice of hepatic origin (20000009) • Broad and narrow terms in the Hepatitis, non-infectious (20000010) • Broad and narrow terms in the Hepatic failure, fibrosis and cirrhosis and other liver damage (20000013) • Narrow terms in the Liver-related coagulation and bleeding disturbances (20000015) 	
P2 Main Study Safety Population (Fisher’s exact test) and All Ixekizumab Safety Population (Summary): TEAE by PT within SMQ or sub-SMQ Listing: TEAE (display in Spotfire)

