	
Elevations in hepatic laboratory tests (ALT, AST, ALP, total bilirubin) using Performing Laboratory Reference Ranges are defined as:
 
 • Include scheduled visits, unscheduled visits, and repeat measurements. • ALT or AST: maximum postbaseline measurement ≥ 3 times (3\times), 5 times (5\times), 10 times (10\times), and 20 times (20\times) the Performing Lab ULN for all patients with a postbaseline value. 
 ○ The analysis of 3\times ULN will contain 4 subsets: patients whose nonmissing maximum baseline value is $\leq 1 \times$ ULN, patients whose maximum baseline is $>1 \times$ ULN but $<3 \times$ ULN, patients whose maximum baseline value is $\geq 3 \times$ ULN, and patients whose baseline values are missing. ○ The analysis of 5\times ULN will contain 5 subsets: patients whose nonmissing maximum baseline value is \leq to $1 \times$ ULN, patients whose maximum baseline is $>1 \times$ ULN but $<3 \times$ ULN, patients whose maximum baseline is $\geq 3 \times$ ULN but $<5 \times$ ULN, patients whose maximum baseline value is $\geq 5 \times$ ULN, and patients whose baseline values are missing. ○ The analysis of 10\times ULN will contain 6 subsets: patients whose nonmissing maximum baseline value is $\leq 1 \times$ ULN, patients whose maximum baseline is $>1 \times$ ULN but $<3 \times$ ULN, patients whose maximum baseline is $\geq 3 \times$ ULN but $<5 \times$ ULN, patients whose maximum baseline is $\geq 5 \times$ ULN but $<10 \times$ ULN, patients whose maximum baseline value is $\geq 10 \times$ ULN, and patients whose baseline values are missing. ○ The analysis of 20\times ULN will contain 7 subsets: patients whose nonmissing maximum baseline value is $\leq 1 \times$ ULN, patients whose maximum baseline is $>1 \times$ ULN but $<3 \times$ ULN, patients whose maximum baseline is $\geq 3 \times$ ULN but $<5 \times$ ULN, patients whose maximum baseline is $\geq 5 \times$ ULN but $<10 \times$ ULN, patients whose maximum baseline is $\geq 10 \times$ ULN but $<20 \times$ ULN, patients whose maximum baseline value is $\geq 20 \times$ ULN, and patients whose baseline values are missing. • Total bilirubin: The number and percentages of patients with a total bilirubin measurement $\geq 1.5 \times$, and 	
Listing: Elevations in hepatic laboratory tests (display in Spotfire)

Special Safety Topic	Definition/Derivation	Analysis/Summary/Listing

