	
Elevated hepatic criteria: maximum ALT ≥3× ULN, maximum total bilirubin ≥2× ULN.
	

Special Safety Topic	Definition/Derivation	Analysis/Summary/Listing
	
Listing of patients who meet any of the following criteria:
 
 • Elevated hepatic criteria: defined as maximum ALT $\geq 3 \times$ ULN, maximum total bilirubin $\geq 2 \times$ ULN • An ALT or AST $\geq 3 \times$ ULN • An ALP $\geq 1.5 \times$ ULN • A total bilirubin $\geq 2 \times$ ULN 
The listing will include: patient demographics, concomitant medications, ALT/AST/ALP/total bilirubin/GGT by visit, treatment start and stop dates, and reason for treatment discontinuation
 
Evaluation of Drug-Induced Serious Hepatotoxicity (eDISH) plot: use maximum ALT measurement and maximum total bilirubin measurement with patients having at least 1 postbaseline ALT and total bilirubin, which contributes 1 point to the plot. The measurements do not need to be taken at the same blood draw.
	
P2 Main Study Safety Population and All Ixekizumab Safety Population: eDISH plot (display in Spotfire)

Cytopenias	
Cytopenias are defined using the PTs from the following 2 sub-SMQs of the Haematopoietic cytopenias SMQ (20000027) as defined in MedDRA version:
 
 • Broad and narrow terms in the Haematopoietic leukopenia (20000030) • Broad and narrow terms in the Haematopoietic thrombocytopenia (20000031) 	
P2 Main Study Safety Population (Fisher’s exact test) and All Ixekizumab Safety Population (Summary): TEAE by PT within sub-SMQ Period 5 (Summary): FEAE by PT within sub-SMQ Listing: TEAE (display in Spotfire)

Infections	
Infections are events including all infections (defined using all the MedDRA PTs from the Infections and infestations SOC), serious infections, potential opportunistic infections, and infections resulting in anti-infective medication administration (i.e., antibacterial, antiviral, antifungals, antiparasitic treatment.). The relationship between TEAEs-infections and other clinical, laboratory, and hematology parameters will be examined using Spotfire tool.
	
P2 Main Study Safety Population (Fisher’s exact test) and All Ixekizumab Safety Population (Summary): TEAE by PT* SAE by PT* DCAE by PT*
 
* Included in overall TEAE tables.

Special Safety Topic	Definition/Derivation	Analysis/Summary/Listing
		
Listing: TEAE (display in Spotfire)

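### ALT, AST, bilirubin and ALP are dropped from the laboratory high/low summary in every safety population, but the hepatic analysis replacing it is not assigned to the etanercept-comparison or randomized-withdrawal populations

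*SAP*

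**What the plan says.** SAP 6.14.4 says that patients with a treatment-emergent or follow-up-emergent "abnormal high or low for laboratory tests will be summarized by treatment group for each safety population", with Fisher's exact test between groups. A bullet beneath it takes out four tests: ALT, AST, total bilirubin and ALP "will not be included in the treatment-emergent abnormal high or low summary as a separate analysis addressing the risk of liver injury" is set out in Table RHCD.6.7. The exclusion is not limited to any population.

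SAP 6.14.3.1 sets the scope of Table RHCD.6.7. The special safety topics "will be presented by treatment group for P2 Main Study Safety Population and All Ixekizumab Safety Population". The only extension comes as an exception: in general, "AESI summary will not be provided for Follow-Up Population during Period 5 except for cytopenia and hepatic laboratory tests".

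The hepatic rows of the table add no further population. The hepatic adverse-event row names the same two. The output column for the elevation row reads only "Listing: Elevations in hepatic laboratory tests (display in Spotfire", with no population. The plot row reads "P2 Main Study Safety Population and All Ixekizumab Safety Population: eDISH plot (display in Spotfire".

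SAP 6.14 defines two more safety populations. The P2 Addendum Safety Population has all pairwise comparisons among ixekizumab, etanercept and placebo. The P4 Randomized Withdrawal Population compares ixekizumab with placebo. Both are to have selected safety data analysed. SAP 6.14.1 lists them beside the main-study and all-ixekizumab populations.

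The safety endpoints in Table RHCD.4.1 include "laboratory values (hematology and chemistry [including ALT and AST", over the course of the study.

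**The concern.** The exclusion in 6.14.4 rests on one reason, that the four tests are analysed elsewhere. If the other analysis does not reach a population, the reason fails there and the tests drop out of the categorical laboratory output by accident. In the same population, every other laboratory test keeps its count and its Fisher comparison.

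At stake is the comparison of liver-test elevations between ixekizumab and etanercept in Period 2, and between continued ixekizumab and placebo in Period 4. These tests matter to the plan: the endpoint table names ALT and AST, and seven entries in Table RHCD.6.12 (D1 to D7) rest on ALT, AST or ALP.

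The remaining by-arm outputs are weaker for this purpose. In arms of 15 to 30 subjects, a difference in means can hide a few large elevations. An adverse-event table counts an elevation only if the investigator reports it. Etanercept is open label, and the blinded assessor in the addendum covers efficacy assessments only, whereas a laboratory count does not depend on reporting.

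**Working it through.** No sample-size or power figure enters this point. The check sets each planned laboratory output against the populations named for it.

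| Safety population | High/low summary, other tests (6.14.4) | High/low summary, four liver tests (6.14.4) | Hepatic laboratory analysis (6.14.3.1, Table RHCD.6.7) |
|---|---|---|---|
| P2 Main Study (ixekizumab vs placebo) | yes | removed | yes |
| P2 Addendum (ixekizumab, etanercept, placebo) | yes | removed | not named |
| P4 Randomized Withdrawal (ixekizumab vs placebo) | yes | removed | not named |
| All Ixekizumab (single group) | yes | removed | yes |
| Follow-Up (Period 5) | yes | removed* | yes, by the exception |

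*The exclusion is worded for the treatment-emergent summary. The Period 5 exception covers hepatic tests in either case.

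The substitute is therefore missing in 2 of 5 populations. These are the two comparisons that the addendum introduced.

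**Could another output fill the gap?**

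- *P2 Main Study.* SAP 6.14 limits its comparison to ixekizumab versus placebo. Table RHCD.6.2 lists etanercept among the Period 2 groups, but it does not separate main from addendum populations; 6.14 does, and gives the etanercept comparisons to the addendum population.
- *All Ixekizumab.* Table RHCD.6.1 includes addendum patients who received ixekizumab, so their elevations are within scope. Table RHCD.6.2 gives no comparison. Baseline for a former etanercept subject is the last value before the first ixekizumab dose (6.1.2), and exposure counts ixekizumab treatment periods only (6.14.1). Time on etanercept or on withdrawal placebo is not part of it.
- *ANCOVA of laboratory values* (6.1.3.2 and 6.1.3.4). This yields mean differences, not counts above a limit.
- *Fisher's test for other categorical safety data* (same sections). This names a method. It does not commit to a liver-test table.
- *Adverse-event tables.* Treatment-emergent events by SOC and PT (6.14.2) and serious events by SOC and PT (6.14.3) are planned for both populations. They include an elevation only if it is reported as an event.
- *Listings* (Table RHCD.6.7). Patient-level hepatic listings name no population, so individual cases may be visible, but not as a count by arm.

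**Size** (SAP 5.2.2). The addendum comparison has 30 + 30 + 15 = 75 subjects, and the withdrawal comparison 20 + 20 = 40. Without any laboratory threshold count are the etanercept arm (about 30) and the withdrawal-placebo arm while on placebo (about 20). These should not be added as distinct subjects: Table RHCD.6.10 allows an etanercept subject to be re-randomized to placebo at Week 60.

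**The case against.** The strongest reply is that the narrower scope is deliberate. SAP 6.14 promises only selected safety data for these two populations. The leukocyte and platelet shift tables, the vital-sign summaries, the CDRS-R analyses and the special-topic rows all leave them out. The addendum objectives in Table RHCD.4.2 concern efficacy, and the ALT/AST endpoint belongs to an objective about the safety of ixekizumab. How much comparative safety output a 30-subject open-label reference arm needs is partly a matter of judgement.

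This lowers the severity but does not remove the inconsistency. Section 6.14.4 does not rely on selection: it covers "each" safety population in its own words ("will be summarized by treatment group for each safety population") and justifies the exclusion solely by a substitute that is absent here. A deliberate reduction would hardly keep every other chemistry test and drop these four.

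A second reply is that 6.14.3.1 lets the program safety analysis plan supersede the SAP on special safety topics without an amendment. That plan is not among the documents and could close the gap. The clause does not show that it does.

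A reader might also infer that liver safety goes unexamined in the randomized comparisons, or that all 75 and 40 subjects go uncounted. The documents do not support either reading. The main Period 2 comparison is in scope, ixekizumab-exposed addendum patients fall within the All Ixekizumab analysis, and adverse-event tables and listings remain.

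**Conclusion.** The point holds as an internal inconsistency with a practical consequence. Followed as written, the SAP produces no laboratory-based by-arm count of ALT, AST, total bilirubin or ALP elevations in either addendum comparison, while other laboratory tests in the same populations get one. What is missing is the comparison in both populations, and any threshold count at all for etanercept and for withdrawal placebo while on placebo.

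Severity is minor to moderate. No efficacy result or type I error rate is affected, and nothing in the documents suggests that a liver signal exists or would be concealed.

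The conclusion assumes that the scope sentence in 6.14.3.1 governs the hepatic laboratory rows that name no population, and that the program safety analysis plan has not already added these populations. It also takes the main Period 2 population as covered on the strength of that scope sentence and the counts described in the table's definition column, since the output column for the elevation row names only a listing.

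**What to change.** In 6.14.4, limit the exclusion of the four tests to populations in which the Table RHCD.6.7 hepatic laboratory analysis is run. For the P2 Addendum and P4 Randomized Withdrawal populations, do one of two things:

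- keep the four tests in the high/low summary; or
- produce the existing Table RHCD.6.7 elevation counts by arm, and name the two populations in 6.14.3.1.

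The options differ. The high/low summary counts values above the upper limit of normal, while the ALT and AST elevation counts start at 3 times that limit. If the second is chosen, the shift categories already defined in the table would show the range between.

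For Period 4, state how values obtained after a relapsing placebo subject starts ixekizumab are handled. At the planned 85% relapse rate this concerns about 0.85 × 20 = 17 placebo subjects.

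SAP Section 3 records that Version 3 was approved after the primary database lock, so any Period 2 table added now should be labelled as added after that lock.

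The main change is one sentence, with a short Period 4 rule and two small tables built from existing definitions. The drawback is slightly more output with low counts, which should be read descriptively.

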6.14.4.1. Leukocytes (White Blood Cells [WBCs]) and Platelets

Further analyses will be conducted for total leukocytes, neutrophils, platelets, lymphocytes, monocytes, eosinophils, and basophils. Neutrophils will include both segmented neutrophils and absolute neutrophils (derived by adding segmented neutrophils and band neutrophil).

The segmented neutrophils and absolute neutrophils will be summarized using the same categories.

Shift table will be produced showing the number and percentage of patients shifting from baseline to a minimum postbaseline result in each relevant category by treatment groups P2 Main Study Safety Population, All Ixekizumab Safety Population, and Follow-Up Safety Population:

- Scheduled visits, unscheduled visits, and repeat measurements will be included.
- Baseline is defined as the minimum result during the defined baseline period or baseline.
- Use the minimum nonmissing postbaseline value within each study period.
- The parameters and categories are:
 - Leukocytes: $\geq 1 \times \text{LLN}$, $< \text{LLN}$ to $\geq 3.0 \times 10^9/\text{L}$, $< 3.0 \times 10^9/\text{L}$ to $\geq 2.0 \times 10^9/\text{L}$, $< 2.0 \times 10^9/\text{L}$ to $\geq 1.0 \times 10^9/\text{L}$, and $< 1.0 \times 10^9/\text{L}$
 - Neutrophils: segmented neutrophils and absolute neutrophils; $\geq 1 \times \text{LLN}$, $< \text{LLN}$ to $\geq 1.5 \times 10^9/\text{L}$, $< 1.5 \times 10^9/\text{L}$ to $\geq 1.0 \times 10^9/\text{L}$, $< 1.0 \times 10^9/\text{L}$ to $\geq 0.5 \times 10^9/\text{L}$, and $< 0.5 \times 10^9/\text{L}$
 - Platelets: $\geq 1 \times \text{LLN}$, $< \text{LLN}$ to $\geq 75.0 \times 10^9/\text{L}$, $< 75.0 \times 10^9/\text{L}$ to $\geq 50.0 \times 10^9/\text{L}$, $< 50.0 \times 10^9/\text{L}$ to $\geq 25.0 \times 10^9/\text{L}$, and $< 25.0 \times 10^9/\text{L}$
 - Lymphocytes: $\geq 1 \times \text{LLN}$, $< \text{LLN}$ to $\geq 0.8 \times 10^9/\text{L}$, $< 0.8 \times 10^9/\text{L}$ to $\geq 0.5 \times 10^9/\text{L}$, $< 0.5 \times 10^9/\text{L}$ to $\geq 0.2 \times 10^9/\text{L}$, and $< 0.2 \times 10^9/\text{L}$
- The LLNs are defined by as follow:
 - Leukocytes: $\text{LLN} = 4.0 \times 10^9/\text{L}$
 - Neutrophils: $\text{LLN} = 2.0 \times 10^9/\text{L}$
 - Lymphocytes: $\text{LLN} = 1.1 \times 10^9/\text{L}$
 - Platelets: $\text{LLN} = 150 \times 10^9/\text{L}$
- With additional categories:

- Decreased; postbaseline category < baseline category
- Increased; postbaseline category > baseline category
- Same; postbaseline category = baseline category.

The change from minimum baseline to minimum postbaseline result for each of these leukocytes and platelets will be summarized graphically using a box plot for P2 Main Study Safety Population.

